1.3 SCHEDULE OF ACTIVITIES (SOA)

Procedures	Screening Phase - 4 weeks	Study Visit 1 (Enrollment/Baseline) Week 1 +/- 2 weeks*
Screening Questionnaire	X	
Review Medical Records	X	
Demographics	X	
Informed consent		X
History and Physical Exam, Cardiology Evaluation		X
Concomitant medication review		X
Vital signs		X
ECG, Echo, PFT, Chest CT, Neuromuscular Ultrasound		X
Biospecimen Collection (blood and urine) ^a		X
Physical Assessment (6MWT, SPPB/Mini-BEST, CPET)		X
VAS-CFS and Qualitative interviews ^b		X
Patient-reported Outcomes and QOL		X
Physical activity and sleep quality monitoring		X
Other assessments (e.g. neurology, vascular function)		X
Optional assessments (brain MRI, skin biopsies)		X
Randomization		X
Adverse event review and evaluation		X
Complete Case Report Forms (CRFs)		X
^a Including urine pregnancy test (women of childbearing potential); ^b Repeated before and up to 72 hours after the CPET		
*May extend to 30 days from enrollment		

Abbreviated Title: Exercise and COVID-19
Version Date: 3/18/2025

Continued: SOA for AET+ group

	Intervention Period 1 Week 3 +/- 1 week	Study Visit 2 (10-week follow-up) Week 14 +/- 4 weeks	3-month follow-up 1 Week 30 +/- 1 week	3-month follow-up 2 Week 43 +/- 1 week	3-month follow-up 3 Week 56 +/- 1 week	3-month follow-up 4 Week 69 +/- 1 week
Procedures						
History and Physical Exam, Cardiology Evaluation		X				
Concomitant medication review		X				
Vital signs	X	X				
ECG, Echo, PFT, Chest CT, Neuromuscular Ultrasound		X				
Biospecimen Collection (blood and urine) ^a		X				
Physical Assessment (6MWT, SPPB/Mini-BEST, CPET)		X				
VAS-CFS and Qualitative interviews ^b		X				
Patient-reported Outcomes and QOL		X	X	X	X	X
Physical activity and sleep quality monitoring	X	X	X	X	X	X
Other assessments (e.g. neurology, vascular function)		X				
Optional assessments (skin biopsies)		X				
Supervised Exercise Session (thrice weekly)	X					
Education Sessions (weekly)	X					
Adverse event review and evaluation	X-----					X
Complete Case Report Forms (CRFs)	X-----					X
^a Including urine pregnancy test (women of childbearing potential); ^b Repeated before and up to 72 hours after the CPET						

Abbreviated Title: Exercise and COVID-19
Version Date: 3/18/2025

Continued: SOA for CON group

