3 OBJECTIVES AND ENDPOINTS

OBJECTIVES	ENDPOINTS	JUSTIFICATION FOR ENDPOINTS
Primary		
#1. To examine the effect of aerobic exercise training (AET) on physical function in participants recovering from COVID-19	Physical function is represented by the distance walked (in meters) during a 6 minute walk test (6MWT) as the primary outcome. Other measures of physical function include the time to exhaustion on the CPET and the SPPB/Mini-BEST score. All physical function outcomes will be measured at baseline and after the AET and CON regimens, and after crossover in the CON group.	The 6MWT distance has been used to reflect longitudinal changes in physical function among patients with ARDS (17 , 58) and SARS (18 , 59), and to detect changes due to exercise participation in patients recovering from SARS (26). In the only study found to date that utilized a training intervention in patients with COVID-19, the 6MWT was used in the RCT to examine changes in exercise capacity following 6 weeks of respiratory training (60).

OBJECTIVES	ENDPOINTS	JUSTIFICATION FOR ENDPOINTS
		A minimal important difference (MID) has yet to be established among survivors of COVID-19. We will consider 30 meters as the MID for this study based on reported ranges of 20 to 30 meters in patients with idiopathic pulmonary fibrosis (61 , 62) and ARDS (63).
Secondary		
#2. To examine the effect of AET on patient reported outcomes and other health-related quality of life (QoL) components in participants recovering from COVID-19	Patient reported outcomes related to fatigue, sleep, post-exertional malaise, post-traumatic stress disorder, depression, anxiety, general and COVID-19 specific QOL outcomes. These outcomes are measured at baseline and after the AET and CON regimens, after crossover in the CON group, and every 3 months for 1 year.	There are currently no studies available regarding the effect of exercise on these outcomes on recovery from COVID-19. It is expected that QOL will be improved with AET as aerobic exercise has been associated with improvements in patient-reported outcomes and health-related QOL in the lung disease population (64-66).

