#3. To examine the effect of AET on free-living physical activity and sleep quality in participants recovering from COVID-19	Quantification of free-living physical activity and sleep quality using wearable accelerometer device. These outcomes are captured upon study entry, throughout the AET and CON regimens, and throughout crossover in the CON group. Outcomes will also be captured every 3 months for 1 year.	Physical activity has been reported to be lower as a result of the COVID-19 pandemic due to public health guidance and governmental measures implemented worldwide (67), and poor sleep quality have been observed among the general population (68) and healthcare workers (69). There are currently no studies available regarding the effects of exercise on these measures on recovery from COVID-19. It is expected that both physical activity and sleep quality will be improved with AET as aerobic exercise is

OBJECTIVES	ENDPOINTS	JUSTIFICATION FOR ENDPOINTS
		associated with greater physical activity (64) in patients with lung disease, and better sleep quality (70) in older adults.
Exploratory		
#4. Explore the effect of AET on clinical outcomes, cardiorespiratory function, cognition, biomarkers, metabolomics, ultrasound-based muscle measurements, vascular and autonomic function in participants recovering from COVID-19	Clinical outcomes (such as cardiac and lung function), cardiorespiratory function, cognition, biomarkers, metabolomics, ultrasound-based muscle measurements, vascular and autonomic function. These outcomes are measured at baseline and after the AET and CON regimens, and after crossover in the CON group.	It is unknown to what degree COVID-19 affects these exploratory outcomes and there are currently no studies available regarding the effect of exercise on recovery from COVID-19. It is likely that AET will result in improvements for these exploratory outcomes based on findings in other populations that demonstrate improved clinical outcomes (71), cardiorespiratory function (64), cognition (72), biomarkers (73), metabolomics (74), muscle measurements (75) and vascular (76) and autonomic (77) function with exercise training.

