6.2 MEASURES TO MINIMIZE BIAS: RANDOMIZATION AND BLINDING

Participants will be randomized to either education (CON arm) or exercise + education (AET+ arm). Due to the nature of the intervention, participants will not be blinded to their treatment allocation. Study personnel will be blinded through initial baseline screening/testing and randomization, however following randomization, due to the nature of exercise training and the time points involved in this study, the blinding process will no longer be possible.

We will use random block-size randomization (with block sizes randomly varying between 4 and 6) to keep groups as equal in number as possible and to avoid early filling of one of the groups. To minimize bias, an independent randomizer who is not affiliated with this study in any other way, will perform randomization of participants.

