The primary outcome variable is the 6MWT distance. The distance-saturation product (DSP) will be calculated as the ratio between total distance walked and lowest SpO₂ value, in those that performed the 6MWT on room air (116). The performance fatigability index will be calculated as the ratio of the 1.5-minute walking speed to the walking speed calculated over the entire 6 minutes of the test divided by the total distance covered on the test. The perceived fatigability index will be calculated by having the participant rate their feeling of tiredness prior to the 6MWT and measuring the change in tiredness after the 6MWT. The change in tiredness divided by the total distance walked will be computed as the perceived fatigability index (114). Heart rate variability will also be examined using the ECG data.

8.3.5.2 Short Physical Performance Battery (SPPB) and the Mini Balance Evaluation Systems Test (Mini-BEST)

The SPPB is a battery of assessments to evaluate lower extremity function and includes balance, gait speed and chair stand tests. While designed for older adults, it has also been used in chronic conditions such as pulmonary disease (117) and survivors of acute respiratory failure (118). It is a recommended COVID-19 core outcome measure of physical function by the American Physical Therapy Association (APTA) (119).

The Mini-BEST is a battery of performance measures that evaluates balance deficits in areas such as anticipatory postural adjustments, reactive postural control, sensory orientation and dynamic gait. It has been used to detect balance disorders across various neurologic conditions, and recommended as a research outcome measure by the Academy for Neurologic Physical Therapy (ANPT) ([120](#)).

The SPPB and the mini-BEST may be utilized for assessing lower mobility strength, gait and balance in participants. The SPPB may be more appropriate for those with more severe physical deficits and the Mini-BEST for higher functioning individuals. Participants scoring high on these assessments at the baseline visit may not need to perform these at follow-up study visits.

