8.3.7.3 Autonomic Nervous System (ANS) Testing

Dysfunction of the ANS have been observed among individuals following COVID-19 infection ([131](#), [132](#)). In particular, autonomic dysfunction is suggested to be contributing to COVID-19 morbidity and mortality ([133](#)) and long-term sequelae experienced by survivors ([134](#)). There are currently no studies reporting on the effect of exercise on autonomic function in survivors of COVID-19.

We aim to perform ANS testing at every study visit, however, participants demonstrating normal function may not need to perform them at subsequent study visits.

- i) The Quantitative Sudomotor Axon Reflex Test (QSART) is a measurement of sympathetic post-ganglionic cholinergic function. It is performed on the Q-Sweat Device (WR Medical Electronics Co., Maplewood, MN) using standard iontophoresis methodology and 10% acetylcholine. Iontophoresis chambers are placed on four sites, the forearm, proximal lateral calf and medial ankle, and foot, and sweat volume is recorded ($\mu\text{l}/\text{mm}^2$).
- ii) Using beat-to-beat blood pressure and heart rate monitoring (WR Medical Electronics, Inc, Maplewood, MN), the following measure are performed: 1) Heart rate-deep breathing is a parasympathetic test performed by having the subject take 6-8 slow deep breaths with 10 seconds per respiratory cycle and measuring the heart rate variability; 2) Valsalva maneuver is a test that involves the sympathetic and parasympathetic system and performed with a forced expiration at 40 mm Hg for 15 seconds and measuring heart rate and blood pressure response; 3) Tilt table testing is performed with a head-up tilt of 70 degrees for 10 minutes after at least 20 minutes in the supine position. Changes in heart rate and blood pressure are continuously recorded during head up tilt and after return to supine position. Published normative values will be used ([135](#)). The hemodynamic criteria for postural orthostatic tachycardia syndrome is a sustained increase of ≥ 30 beats per minute from baseline

heart rate when transitioned from supine to upright position for 10 minutes and in absence of orthostatic hypotension (systolic blood pressure drop of > 20 mm Hg or diastolic blood pressure drop of > 10 mm Hg ([136](#)).

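### Sections 8.3.5.2 and 8.3.7.3 allow follow-up SPPB/Mini-BEST and autonomic tests to be skipped after a high or normal result, in conflict with the endpoint table and with no cut-off

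*Combined protocol and SAP*

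**What the plan says.** **Measured after each regimen.** Section 3, objective #1, names the SPPB/Mini-BEST score among the physical function measures and states: "All physical function outcomes will be measured at baseline and after the AET and CON regimens, and after crossover in the CON group". For objective #4, which includes autonomic function: "These outcomes are measured at baseline and after the AET and CON regimens, and after crossover in the CON group". Section 4.1 has both groups repeat at 10 weeks the assessments done at baseline. The schedule of activities (section 1.3) marks the physical assessment row, which names SPPB/Mini-BEST, at Visit 2 in both arms and at Visit 3 in CON, with no condition attached. Autonomic testing is not named there; it would fall under the row for other assessments, which gives neurology as an example.

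**May be skipped.** Section 8.3.5.2: "Participants scoring high on these assessments at the baseline visit may not need to perform these at follow-up study visits". Section 8.3.7.3: "participants demonstrating normal function may not need to perform them at subsequent study visits".

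**Choice of battery.** Section 8.3.5.2 also says "The SPPB and the mini-BEST may be utilized for assessing lower mobility strength, gait and balance in participants". It suggests the SPPB for more severe deficits and the Mini-BEST for higher-functioning people.

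**Related text.** The opening of section 8.3 places research assessments at all study visits unless specified otherwise. It treats omissions as expected if they are not the primary outcome and are not needed for the training range or for safety. Section 6.2 keeps staff blinded through baseline testing and randomization, after which "the blinding process will no longer be possible". Section 9.4.9 plans a baseline-adjusted ANCOVA of Visit 2 values for objective #4. Section 9 names no analysis for SPPB/Mini-BEST and has no rule for skipped tests.

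**The concern.** The two skip sentences make missingness depend on the outcome's own earlier value. That differs from a participant who happens not to finish a long list of tests.

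Three things are at stake for these measures. First, change on these tests is not observed in anyone skipped. Section 8.3.7.3 itself notes that no studies report the effect of exercise on autonomic function in COVID-19 survivors, so its direction in people with normal function cannot be presumed. Second, a comparison among those retested estimates the effect in low or abnormal scorers, whereas the objectives are framed for participants in general. Third, numbers fall in a trial with 38 completers per arm.

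A further weakness is discretion. Neither section gives a numeric threshold, says who decides, or says when. Nor does any rule keep a participant on the same battery across visits, so a baseline SPPB could be followed by a Mini-BEST.

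**Working it through.** **1. The plan's own figure.** Section 9.2 gives a difference of 77.4 − 20.7 = 56.7 m, SDs of 98.6 and 71.3 m, significance level 0.05 (taken as two-sided) and 80% power. An unequal-variance t-test gives power 0.798 at 37 per arm and 0.808 at 38, so 38 per arm reproduces. Allowing for 85% completion, 76 / 0.85 = 89.4, so 90 randomized also reproduces. This calculation covers the 6-minute walk only. Section 8.3.5.1 requires that test at every study visit, so the skip sentences do not touch it.

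**2. Lost precision.** The skipped share is not in the documents and is assumed here. If a share f is skipped in each arm, the standard error of the arm difference is multiplied by 1/√(1 − f):
- f = 0.50: 1/√0.50 = 1.41
- f = 0.70: 1/√0.30 = 1.83

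Starting from 38 per arm, the difference detectable with 80% power (two-sample t-test, two-sided 0.05) is:

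| Skipped | Left per arm | Detectable difference |
|---|---|---|
| 0% | 38 | 0.65 SD |
| 25% | 28 | 0.76 SD |
| 50% | 19 | 0.93 SD |
| 75% | 10 | 1.33 SD |

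**3. Change of estimand.** Suppose, for illustration only, an effect of +0.3 SD in low scorers and −0.3 SD in high scorers. The retested subset shows +0.30 SD whatever the share skipped. The effect in all participants is 0.3(1 − f) − 0.3f:
- f = 0.25: 0.225 − 0.075 = +0.15 SD
- f = 0.50: 0.15 − 0.15 = 0.00 SD
- f = 0.75: 0.075 − 0.225 = −0.15 SD

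**4. Does skipping bias the arm comparison?** I simulated 400,000 participants with baseline-to-follow-up correlation 0.6 and no true effect, analysed by baseline-adjusted ANCOVA, with 25%, 50% or 75% above the cut-off.
- Fixed baseline cut-off applied to both arms: bias about 0.00 SD in every case.
- High scorers retested only in CON, and only when their follow-up value is below average: bias 0.06, 0.12 and 0.11 SD in favour of AET+.

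The second case shows what unregulated discretion could do. Nothing in the documents says it will happen.

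**5. Regression to the mean.** Take a normally distributed score, correlation r and no true change. The mean Visit 1 to 2 change in those retested is 0.798(1 − r) SD if the upper half is skipped and 1.159(1 − r) SD if the upper 70% is skipped. At r = 0.6, 0.7 and 0.8 this gives 0.32, 0.24 and 0.16 SD, or 0.46, 0.35 and 0.23 SD. For Visit 2 to 3 after selection on Visit 1, the multiplier becomes (r12 − r13), the correlations of Visit 1 with Visits 2 and 3. If these are equal, the drift is zero.

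**The case against.** The strongest reply is that section 8.3 already allows for this. Assessments occur at all visits unless specified otherwise, non-primary omissions are expected, and sections 8.3.5.2 and 8.3.7.3 are such specifications. This stands in part: omitting these tests would not surprise anyone working from section 8. But it does not amend section 3 or section 4.1, which carry no exception, and it does not deal with selection on the outcome itself.

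Further points on the other side are fair:
- Both sentences say the tests may not be needed. Full retesting remains allowed.
- The schedule conflict for autonomic tests is only indirect.
- A reader might infer that worsening in skipped participants would be invisible. That goes too far. The 6-minute walk and the cardiopulmonary exercise test are done at every study visit, and follow-up includes a brief examination, PROMIS physical function and adverse event enquiry. Only change on the skipped tests is unseen.
- A reader might also infer that regression to the mean inflates the trial's results, including the CON Visit 2 to 3 change. The documents do not support that for SPPB/Mini-BEST. No Visit 1 to 2 within-arm test is planned, the rule selects on Visit 1, and Visit 2 to 3 drift then arises only if correlation decays with time. The autonomic rule is not tied to baseline, so a normal Visit 2 result could excuse Visit 3; drift in that comparison remains possible.
- Repeat autonomic testing is a real burden: sweat testing at four sites, deep breathing, Valsalva, and at least 20 minutes supine plus 10 minutes of tilt. Sparing people with normal results is defensible for an exploratory endpoint.

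**Conclusion.** The conflict in the text is real and worth correcting. Its reach is limited to a supporting physical function measure and an exploratory outcome; the primary analysis and the 38 per arm stand.

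If the permission is used, the loss is of two kinds: the comparison is confined to low or abnormal scorers, and the standard error rises by 1.41 with half skipped or 1.83 with 70% skipped. Those shares are assumptions, as are the effect sizes and correlation in the illustrations.

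A reader might infer that unblinded staff choose who is retested. The documents do not say so. The SPPB/Mini-BEST criterion is a baseline score, obtained while staff are blinded, and a fixed cut-off applied equally to both arms would leave the ANCOVA valid within that subset. What can be said is that no cut-off, decision-maker or decision time is set and staff are unblinded by Visit 2, so retesting could differ by arm.

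**What to change.** **SPPB/Mini-BEST.** Delete the skip sentence in section 8.3.5.2. State that each participant repeats at Visit 2, and in CON at Visit 3, the battery used at baseline, and that the two scales are analysed separately.

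**Autonomic tests.** Either do the same in section 8.3.7.3, or:
- set a numeric baseline criterion, stating which tests it covers;
- record before randomization who will be retested;
- amend section 3 and the schedule to match, naming autonomic testing there;
- limit the autonomic conclusion to the baseline-abnormal subset.

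**Cost.** A wording amendment, plus extra testing time at visits where assessment is already scheduled. The added time is small for SPPB/Mini-BEST and larger for the autonomic tests, which is why the criterion-based route is acceptable for them.

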8.3.5.3 Cardiopulmonary Exercise Test (CPET)

The CPET will be obtained at every study visit. Participants will complete an incremental ramp protocol on the treadmill or cycle ergometer where the work rate will be gradually increased until volitional fatigue is reached by the participant. The ramp rate used will be based on participants' responses to their current physical activity habits. Participants will perform the CPET on room air, unless they were prescribed O₂, in which case, supplemental O₂ will be provided during the test using the same delivery device and flow at each test to maintain consistency. Rating of perceived dyspnea and rating of perceived exertion will be asked and recorded throughout the test.

This is a symptom-limited test in which the target endpoint is exertional intolerance defined as the participants expressed desire to stop exercising despite strong verbal encouragement from the testing staff. Other symptomatic endpoints for stopping the exercise test will be those recommended by the ACSM. Additionally, should any participant's O₂ saturation decrease to <80%, the test will be terminated with or without the presence of symptoms of severe dyspnea. Blood glucose of diabetic participants will be monitored before and after testing, and as clinically necessary. Testing will be performed by qualified staff using an NIH glucometer.

The CPET will be performed on a treadmill or cycle ergometer interfaced with the Medgraphics Cardio2 Ultima® CPX system for automatic increment of the work rate. A facemask placed over the lower portion of the participant's face (mouth and nose) or a mouthpiece and nose-clip will house the interface for pulmonary gas exchange measurements. For participants prescribed O₂, this test may be performed without collecting gas exchange as modified oxygenation may produce inaccurate gas exchange variables ([121](#)). Heart rate will be obtained in all participants from ECG recordings and electrodes will be placed on the participants' chests in the standard Mason-Likar exercise testing configuration. ECG will be monitored and recorded continuously throughout the test and recovery.

Key variables measured by the CPET include peak O₂ uptake (VO₂), the "gold standard" index for global cardiorespiratory function, and the anaerobic threshold (AT), which denotes the point that additional energy sources are required to supplement aerobic metabolism if exercise is to continue. Other gas exchange variables such as CO₂ output (VCO₂), ventilation, respiratory rate, and end-tidal partial pressure of CO₂ and O₂ allows analysis of respiratory and ventilatory responses to exercise. Other variables such as peak respiratory exchange ratio and peak heart rate from ECG will also be measured and recorded to facilitate data analysis. Pulse oximetry and

blood pressure will also be monitored during the CPET. Heart rate variability may also be examined using the ECG data.

